4.10.2 Primary Efficacy Variables

Clinical question of interest: Does the study drug Proxalutamide (GT0918) increase the proportion of subjects who do not experience all-cause hospitalization for at least 24 hours, do not require supplemental oxygen for at least 24h in response to $\text{SpO}_2 \leq 93\%$ and are alive by Day 28, in comparison to placebo?

Intercurrent events (may occur between randomization and Day 28), not mutually exclusive:

- IE1: subject's withdrawal from the study prior to Day 28
- IE2: subject lost to follow-up prior to Day 28
- IE3: subject did not receive any dose of study treatment

Attributes of Estimand (following a treatment policy strategy) [ICH E9 (R1) Addendum 2019]

- Population: all subjects in the mITT population
- Treatment Conditions:
 - condition of interest: randomized to GT0918 + standard of care and treated
 - alternative/control condition: randomized to placebo + standard of care and treated
- Endpoint: the proportion of subjects who do not experience all-cause hospitalization (defined as ≥ 24 hours), do not require supplemental oxygen for ≥ 24 h in response to $\text{SpO}_2 \leq 93\%$ and are alive by Day 28
Note: All-Cause Hospitalization includes: Hospitalization, Emergency room and ICU. Extended Care Facility Admittance is excluded.
- Population-level Summary: estimated incidence probability for subjects not experiencing all-cause hospitalization (defined as ≥ 24 hours), not requiring supplemental oxygen for ≥ 24 h in response to $\text{SpO}_2 \leq 93\%$ and alive by Day 28 (in each treatment group separately)

Main Estimator for Estimand: Odds ratio by Day 28 with adjusting stratification factors defined by baseline clinical status used in the stratified randomization

- Intercurrent events IE1 and IE2 will be disregarded for the inclusion of subjects in the statistical analysis, IE3 restricts the inclusion of subjects to those who received at least one dose of study treatment. Hence, the main estimator for Estimand will be based on the mITT analysis set.
- Subjects with missing primary assessments by day 28 will be treated as meeting primary endpoint. The primary endpoint event rate will be compared between treatment and placebo arm using CMH Chi-square test with adjusting age and the stratification factors (sex, race and ethnicity, and number of risk factors) at time of randomization. The hypothesis test will be performed at the one-sided 0.025 level based on mITT. Odd ratio with 95% exact confidence interval and p-value will be presented.
- The number and proportion of subjects that do not experience any of the 3 components (all-cause hospitalization, requirement of supplemental oxygen and death) of the primary endpoint by Day 28 will be summarized by treatment for the mITT population in frequency tables and listed.
- The individual components of the primary endpoint will be summarized as well.

The following sensitivity analysis will be performed for the primary endpoint:

- Among subjects with dosing days > 7 days;
- Per protocol analysis set;
- Complete case analysis set (subjects without any missing primary endpoint assessments);
- Removing the constraint of ≥ 24 hours in hospitalization and supplemental oxygen use;
- By treating missing primary assessments as hospitalization;
- By treating missing primary assessments as hospitalization and among subjects with dosing days > 7 days.

All sensitivity analyses will be performed using mITT sets except the per protocol analysis. Also, all sensitivity analyses will be conducted using the same one-sided CMH chi-square tests introduced for the primary endpoint analysis.

Interim analysis

An interim analysis will be conducted when 334 subjects complete Day 28 after first dose to assess safety, futility, efficacy, sample size adjustment as well as potential enrichment of the population to enroll a population at higher risk for an infection requiring hospitalization or oxygen support in case the observed rates for the primary endpoint in the control arm are lower than expected. An IDMC will review the unblinded interim analysis report to assess the objectives of the interim analysis and provide recommendations about early study closure, change study population, or change to study sample size.

The one-sided Type I error rate (0.025) for the primary efficacy endpoint will be adjusted following O'Brien and Fleming type alpha spending method. The actual alpha spending will be calculated based on the actual information used for the interim analysis and used as the efficacy boundary, as shown below. The efficacy criterion will be based on the one-sided p-value of the primary endpoint analysis as less than the actual alpha spending. In this case the stopping boundary for efficacy is met and the study could be stopped for efficacy.

$$\text{O'Brien and Fleming: } \alpha_{IA}(t^*) = 2 - 2\Phi(Z_{1-\alpha/2}/\sqrt{t^*}),$$

where IA means interim analysis, Φ denotes the standard normal cumulative distribution function and t^* denotes the fraction of information that has been observed at Interim Analysis timewpoint.

The futility of a study that is underway can be determined by calculating its conditional power, which is the probability of statistical significance at the completion of the study given the data obtained so far. The futility criterion for the study will be based on the conditional power of the study being <10%. The conditional power will be evaluated based on primary endpoint in the interim analysis. If the conditional power of the study at the time interim analysis performed is between 50% to 80% (promising zone approach), the sample size could be increased to a maximum of 1500 subjects based on the efficacy in the interim analysis for overall population. If the conditional power of the study is above 80% power and the stopping boundary for efficacy is not met, the sample size will not be changed. The general lower one-sided conditional power is computed as

$$CP_{IA}(\theta) = \Phi\left(\frac{-Z_{IA}\sqrt{I_{IA}} - z_{1-\alpha}\sqrt{I_{FA}} - \theta(I_{FA} - I_{IA})}{\sqrt{I_{FA} - I_{IA}}}\right),$$

where

IA representing interim analysis and FA representing final analysis,

$\theta = P_2 - P_1$ (the expected difference under the alternative hypothesis),

$Z_{IA} = (p_{2IA} - p_{1IA})\sqrt{\hat{I}_{IA}}$ (the z-statistic computed from the observed data),

$I_{IA} = \frac{1}{\sigma^2} \left(\frac{1}{n_{1IA}} + \frac{1}{n_{2IA}} \right)^{-1}$ (the interim information level),

$I_{FA} = \frac{1}{\sigma^2} \left(\frac{1}{n_1} + \frac{1}{n_2} \right)^{-1}$ (the final information level),

where

p_{jIA} is the sample proportion for group j, estimating p_j at IA,

\hat{I}_{IA} is the estimated information from the sample at IA,

n_{jIA} is the sample size in group j at IA,

n_j is the final sample size in group j,

$\sigma^2 = \bar{p}(1 - \bar{p})$ with $\bar{p} = (P_1 + P_2)/2$

The conditional power calculated based on different software may be slightly different.

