#### **10.8 Interim Analysis**

An interim analysis will be conducted when 334 subjects completed Day 28 after first dose. The objective of the interim analysis to assess safety, futility, efficacy, sample size adjustment as well as potential enrichment of the population to enroll a population at higher risk for an infection requiring hospitalization or oxygen support in case the observed rates for the primary endpoint in the control arm are lower than expected. An independent data monitoring committee (IDMC) will review the unblinded interim analysis report to assess the objectives of the interim analysis and provide recommendations about early study closure, change study population, or change to study sample size. Rigorous steps will be taken (e.g., firewalls) where possible to minimize the information that can be inferred by observers.

The futility criterion for the study will be based on the conditional power of the study being <10%. The efficacy criterion will be based on the one-sided p-value of the primary endpoint analysis as <0.0015. In this case the stopping boundary for efficacy is met and the study could be stopped for efficacy.

The topline safety analysis will include treatment related SAE including death. The IDMC can recommend stopping the study.

The conditional power will be evaluated based on primary endpoint in the interim analysis. IDMC could recommend a change of the subject population to enroll more subjects if the event rate is lower than expected. The IDMC will review the interim efficacy results and in case of substantial treatment differences between subpopulations, e.g., <50 years compared to  $\geq$ 50 years, provide recommendations for modifications of further enrollment. Criteria for those recommendations will be defined in the DMC charter. The consequences of those recommendations on the statistical analysis as well as the samples size adjustment will be summarized in a separate document and attached to the statistical analysis plan.

If the conditional power of the study at the time interim analysis is between 50% to 80% (promising zone approach), the sample size could be increased to a maximum of 1500 subjects based on the

efficacy in the interim analysis for overall population. If the conditional power of the study is above 80% power the sample size will not be changed. The detailed exact rule for sample size re-estimation will be pre-specified in the DMC charter.

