3 INVESTIGATIONAL PLAN

3.1 Overall Study Design and Plan

This is a randomized, placebo-controlled two-arm study with the objective to evaluate the efficacy and safety of GT0918 in outpatients with mild or moderate COVID-19 illness.

The population of subjects with mild to moderate COVID-19 illness will be chosen to evaluate if anti-androgen therapy may effectively prevent progression to the severe form of COVID-19 illness by treating this population early in their disease course and prior to respiratory compromise and failure.

The study is a multicenter trial that will be conducted in the United States (US) and other countries. Approximately 668 subjects will be randomized in a 1:1 ratio to either GT0918 or placebo. There will be an interim analysis after 334 subjects completing Day 28 after the first dose to allow early stopping for futility, efficacy, or safety. The blood samples for PK analysis need to be collected for at least 200 subjects, whom will also be randomized into the interventional treatment or placebo group with 1:1 ratio.

Subjects will be randomized into 1 of 2 arms with 1:1 ratio, each will receive an interventional treatment/placebo.

Randomization will be stratified by the following factors:

- Sex: Male or Female
- Race and ethnicity (non-Hispanic White or others /Hispanic or Latino /non-Hispanic Black)
- Number of risk factors 0, 1-2, ≥ 3 (based on CDC defined conditions <https://www.cdc.gov/coronavirus/2019-ncov/need-extra-precautions/people-with-medical-conditions.html>). Adults of any age with the following conditions are at increased risk of severe illness from the virus that causes COVID-19:
 - Age ≥ 65 years
 - Cancer
 - Chronic kidney disease
 - Chronic lung diseases, including COPD (chronic obstructive pulmonary disease), asthma (moderate to severe), interstitial lung disease, cystic fibrosis, and pulmonary hypertension
 - Dementia or other neurological conditions
 - Down Syndrome
 - Heart conditions, such as heart failure, coronary artery disease, or cardiomyopathies or hypertension
 - Immunocompromised state (weakened immune system) from solid organ transplant
 - Liver disease
 - Overweight and Obesity (body mass index [BMI] ≥ 25 kg/m²)
 - Sickle cell disease or thalassemia
 - Smoking, current or former
 - Diabetes Type 1 or 2
 - HIV infection
 - Solid organ or blood stem cell transplant
 - Stroke or cerebrovascular disease, which affects blood flow to the brain
 - Substance use disorders

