3.2 Planned Interim Analysis

An interim analysis will be conducted when 334 subjects complete Day 28 after first dose. The objective of the interim analysis to assess safety, futility, efficacy, sample size adjustment as well as potential enrichment of the population to enroll a population at higher risk for an infection requiring hospitalization or oxygen support in case the observed rates for the primary endpoint in the control arm are lower than expected. An independent data monitoring committee (IDMC) will review the unblinded interim analysis report to assess the objectives of the interim analysis and provide recommendations about early study closure, change study population, or change study sample size.

The futility criterion for the study will be based on the conditional power of the study being <10%.

The efficacy criterion will be based on the one-sided p-value of the primary endpoint analysis as <0.0015. The boundary is estimated based on O'Brien and Fleming type alpha spending method. In this case the stopping boundary for efficacy is met and the study could be stopped for efficacy. Assuming there is no change in the study design regarding sample size modification, the one-sided p-value of <0.024 will be used for the final analysis to conclude the efficacy of the treatment group.

The conditional power will be evaluated based on primary endpoint in the interim analysis. If the conditional power of the study at the time interim analysis is between 50% to 80% (promising zone approach), the sample size could be increased to a maximum of 1500 subjects based on the efficacy in the interim analysis for overall population. If the conditional power of the study is above 80% power and the stopping boundary for efficacy is not met, the sample size will not be changed.

Rigorous steps will be taken (e.g., firewalls) where possible to minimize the information that can be inferred by observers.

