4.12 Determination of Sample Size

The primary endpoint event rate for the treatment arm is assumed at 97% and for the placebo arm is assumed at 91%.

The sample size was calculated using EAST v6.5 software for a group sequential test for 2 proportions. With a total of 668 subjects the study will have about 90% power at a one-sided 0.025 significance level of the hospitalization or death rate using a Chi-square test with one interim analysis at 50% of the information (when 334 subjects have been observed for 28 days).

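### Interim conditional power is computed at the planned 6-point difference and planned variance, so futility does not register power lost to a low event rate and the promising zone opens on weak trends

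*SAP*

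**What the plan says.** - **Futility and re-estimation (SAP 3.2 and 4.10.2).** "The futility criterion for the study will be based on the conditional power of the study being <10" per cent. If CP lies between 50% and 80%, "the sample size could be increased to a maximum of 1500 subjects based on the efficacy in the interim analysis". Above 80%, with the efficacy boundary not met, the size stays as planned.
- **The CP formula (SAP 4.10.2).** Theta is "the expected difference under the alternative hypothesis". Both information levels use a variance formed from the average of the planned proportions P1 and P2. Only the interim Z uses observed proportions and estimated information. The section gives no numbers for P1 and P2. The only assumed rates are in SAP 4.12: "The primary endpoint event rate for the treatment arm is assumed at 97% and for the placebo arm is assumed at 91" per cent.
- **Low event rates (Protocol 10.8; SAP 3.2 and 4.10.2).** Enrichment towards higher-risk subjects is foreseen "in case the observed rates for the primary endpoint in the control arm are lower than expected". Read with that purpose, this means fewer control-arm events than planned. SAP 4.10.1.1.3 reports hospitalization below 2% in the study.
- **Final level.** Protocol 10.8 gives 0.0245 and SAP 3.2 gives 0.024, each only if the sample size is not changed. Protocol 10.8 leaves the exact re-estimation rule to the DMC charter, and the consequences for the analysis to a separate document.

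**The concern.** CP drives two decisions: whether to stop for futility and whether to raise the sample size to as many as 1500. The formula credits the second half of the trial with a 6-point benefit whatever the interim data show. If the placebo event rate is below 6%, a 6-point reduction in events is arithmetically impossible, yet it is still credited.

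Two things are at stake. A trial that has lost most of its power because events are rare may not be flagged. And the sample size may be more than doubled on a trend that the data themselves barely support. An increase on a weak trend is also where an unweighted final test can exceed its nominal error.

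**Working it through.** **Inputs.** Rates 0.97 and 0.91 (SAP 4.12), so theta = −0.06 in the SAP's sign and σ² = 0.94 × 0.06 = 0.0564. "Approximately 668 subjects will be randomized in a 1:1 ratio to either GT0918 or placebo" (SAP 3.1), so 334 per arm. SAP 4.12 plans "about 90% power at a one-sided 0.025 significance level", "with one interim analysis at 50% of the information (when 334 subjects have been observed for 28 days"), so about 167 per arm at a fraction of 0.5.

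**The plan's own figures.** A pooled two-proportion test needs 328 per arm, 656 in total. Times the group-sequential inflation of 1.0034 this is 658, within 3% of 668. Power at 668 is 0.903 (pooled) to 0.908 (unpooled). The SAP spending formula at 0.5 gives 0.00153 (stated 0.0015), leaving a final level of 0.0245. The design reproduces.

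**SAP conditional power.** I_IA = 83.5/0.0564 = 1480.5 and I_FA = 167/0.0564 = 2961.0, so √(I_FA − I_IA) = 38.48. With Z > 0 favouring GT0918:

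CP = Φ(Z − 1.96√2 + 0.06 × 38.48) = Φ(Z − 2.772 + 2.309) = Φ(Z − 0.463)

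- CP at Z = 0 is Φ(−0.463) = 32%.
- CP < 10% needs Z < −0.82.
- CP of 50% to 80% is Z 0.46 to 1.30, one-sided p about 0.32 to 0.10.

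**Current-trend CP** replaces theta by the interim estimate: Φ(2Z − 2.772). Over the SAP's 50–80% zone it runs from 3.2% to 43.6%. Its own 50–80% zone is Z 1.39 to 1.81.

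| Events, placebo / GT0918 (167 per arm) | Z | SAP CP | Current-trend CP |
|---|---|---|---|
| 15 / 15 | 0 | 32% | 0.3% |
| 3 / 3 | 0 | 32% | 0.3% |
| 0 / 1 | −1.00 | 7% | below 0.1% |
| 2 / 4 | −0.82 | 9.9% | below 0.1% |
| 4 / 2 | 0.82 | 64% | 13% |

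**How often futility stops the trial (exact binomial enumeration).**
- No effect: 20% at a 9% event rate, 23% at 2%, 25% at 1%.
- Placebo 2%, GT0918 0.67% (the planned risk ratio of 1/3): fixed-sample power at 668 is about 32%. The SAP rule stops 4% of such trials; a current-trend rule would stop 35%.

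**Promising zone and type I error.** Under no effect, about 23% of trials fall in the SAP zone. Assume an unweighted final test with critical value c = 1.9686 (0.0245). Given interim Z, it rejects with probability 1 − Φ((c − √t·Z)/√(1 − t)), where t is 0.5 at 668 and 334/1500 = 0.223 at 1500.
- At Z = 0.46, raising the size lifts this from 0.0101 to 0.0236.
- At Z = 1.30 it falls from 0.0695 to 0.0625. The two curves cross at Z = 1.19.

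Most of the SAP zone lies below the crossing, and all of the current-trend zone lies above it. Integrating over the interim Z:

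| Zone and final test | One-sided type I error |
|---|---|
| SAP zone, 1500 throughout, level 0.0245 | 0.0271 |
| SAP zone, 1500 throughout, level 0.024 | 0.0266 |
| SAP zone, size chosen for 80–90% planned CP, level 0.0245 | 0.0260–0.0266 |
| Current-trend zone, 1500 throughout, level 0.0245 | 0.0235 |
| Pre-weighted combination test at 0.0245, either zone | 0.025 |

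Exact enumeration of the first row, unstratified, gives 0.0249 to 0.0268 at event rates of 1–6%.

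**The case against.** CP at the design alternative is a recognised and deliberately cautious basis for futility, because it avoids stopping on an unlucky first half. Low event rates also have a separate route: enrichment at the interim, and an IDMC recommendation to stop for lack of efficacy (Protocol 8.8). Both points stand, so a preference for another effect size is partly judgement. They do not help the promising zone, where a planned-effect CP of 50–80% says little about what the interim data support.

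Two stronger readings are tempting, and the documents do not support them.

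- **That futility cannot act when events are rare.** It can. The interim Z uses observed proportions, so the rule is a cut-off on Z at any event rate. One GT0918 event against none on placebo gives CP of 7%, a stop. Its stopping chance under no effect does not fall as events become rarer. What it lacks is any response to lost power.
- **That the plan as written inflates type I error.** This needs an unweighted final test at the unchanged level. Both stated levels are limited to the case of no size change, and the rule after an increase sits in documents not available here. The text also allows an increase up to 1500, not always to 1500, and by exact enumeration the error at a 2% event rate is 0.0249.

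**Conclusion.** The point holds in limited form. With P1 and P2 read as 0.97 and 0.91, conditional power depends on the interim Z alone. Futility requires GT0918 to look worse than placebo, is lenient at every event rate and does not register a loss of power. The zone that permits up to 1500 subjects corresponds to current-trend CP of 3–44%.

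The type I error consequence is modest and conditional: up to about 0.027 against 0.025 with the ordinary CMH test at the unchanged level, and none with a pre-weighted test. The gap in the visible documents is that the final test after an increase is not stated. The figures assume a split of 167 per arm, a normal approximation except where enumeration is named, and an unstratified test. This is a cheap improvement.

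**What to change.** In SAP 4.10.2, with matching charter wording:

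- **(a) Promising zone.** State P1 and P2 as numbers. Evaluate the 50–80% zone at the interim estimate of the difference with the interim pooled variance. State the final test and level after any increase, for example a pre-weighted combination test. Fewer and stronger trends would then qualify for an increase.
- **(b) Futility.** Apply the design odds ratio, (0.03/0.97)/(0.09/0.91) = 0.31, to the observed control rate with the observed variance, and give a fallback for an interim with no events, where the calculation is undefined. At a 2% control rate the credited GT0918 rate is about 0.63% (odds 0.31 × 0.0204), a difference of about 1.4 points instead of 6.

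The drafting cost is wording only, but (b) changes the rule even at planning rates. At a 9% event rate, stopping under no effect rises from 20% to about 37%, and wrongful stopping under 97% versus 91% rises from 0.07% to about 1.0%. Current-trend CP for futility would be harsher still: 77% and 4.8%.

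If the interim has already been held, report which theta and variance were used, together with current-trend CP.

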4.10.3 Secondary Efficacy Variables

Hospitalization Percentage

Hospitalization percentage is defined as the percentage of subjects who experience any of the following events due to all causes by Day 28:

- Hospitalization for \geq 24 hours or
- Supplemental oxygen for \geq 24 hours in response to $\text{SpO}_2 \leq 93\%$ or
- Death

The same process used for the primary endpoint analysis will be used to compare the difference between treatment groups.

The following sensitivity analysis for hospitalization percentage will be performed among subset of mITT subjects:

- With dosing days > 7 days;
- With one or several major risk factors below:
 - Single risk factor: age (≥ 50 years; ≥ 60 years), major underlying medical conditions (overweight, obesity, hypertension, diabetes, smoking);
 - Combination of age factor in column 1 and other major underlying medical conditions in column 2 in the table below (e.g., age ≥ 50 years and/or obesity at randomization; age ≥ 60 years and/or obesity at randomization);

Age	Major underlying medical conditions
≥ 50 years	Overweight
≥ 60 years	Obesity Hypertension Diabetes Smoking

- With aged ≥ 50 years and days from symptom onset to study randomization ≤ 5 days and days from the positive SARS-CoV-2 Prior to first dosing ≤ 3 days;
- With aged ≥ 50 years and higher than normal biomarkers (CRP, Ferritin, D-dimer).

All sensitivity analyses will be conducted using one-sided CMH chi-square tests used for the primary endpoint analysis. Forest plots for the sensitivity analysis will be presented.

Change from Baseline to Days 3, 7, 14 and 28 in SARS CoV-2 Viral Load

Change of SARS-CoV-2 viral load from baseline, which will be evaluated in log base 10 scale, will be summarized, and plotted by treatment group and listed. Two sample t-tests will be used to compare differences in the change of SARS-CoV-2 viral load between treatment groups at Day 3, 7, 14 and 28, respectively.

Also, an analysis of covariance (ANCOVA) model will be used to compare the change from baseline in SARS-CoV-2 viral load at Day 3 with fixed effects for treatment group, age and stratification factors (sex, race and ethnicity, and number of risk factors), and baseline viral load as a covariate. If systematic pattern is identified from the residual of predicted values, a transformation of the baseline viral load will be employed to improve the performance of the model. Estimated treatment differences

in comparison to placebo along with corresponding two-sided 95% confidence intervals (CIs) and p-values will also be presented.

Additionally, change from baseline in SARS-CoV-2 viral load at Day 3, 7, 14 and 28 will be compared using a mixed model repeated measures (MMRM). The model will include treatment group, visit, treatment-by-visit interaction, age and stratification factors (sex, race and ethnicity, and number of risk factors) as fixed effects, baseline viral load as a covariate, and subject as a random effect. If the unstructured covariance matrix fails to converge, the heterogeneous Toeplitz covariance structure, followed by the heterogeneous autoregressive covariance structure, will be used. If systematic pattern is found in the residual of predicted values, a transformation of the baseline viral load will be employed to improve the performance of the model. Comparisons of GT0918 to placebo for change from baseline in viral load and the corresponding two-sided 95% CIs along with p-values will be calculated and plotted based on the MMRM model at each visit.

Sustained 100% SARS CoV-2 Viral Reduction

SARS-CoV-2 viral reduction (%) is calculated as

$$(\text{viral load after baseline} - \text{viral load at baseline}) / (\text{viral load at baseline}) * 100\%.$$

If the value of SARS-CoV-2 viral reduction is greater than or equal to 100 the result of 100% SARS CoV-2 viral reduction will be set as "Yes". Otherwise, a negative result of "No" will be obtained.

Sustained 100% SARS CoV-2 viral reduction (Yes/No) is defined when at least two consecutive negative ("No") tests (≥ 24 hours apart) are obtained. The date of sustained 100% SARS CoV-2 viral reduction is defined as the earlier date of the consecutive negative tests.

The proportion of subjects that achieve sustained 100% SARS CoV-2 viral reduction at Days 3, 7, 14, and 28 will be summarized by treatment in frequency tables, plotted and listed. Generalized estimating equation (GEE) model will be used to model the proportions of achieving SARS-CoV-2 clearance at different visits. The model will consider treatment group, visit, treatment-by-visit interaction, age and stratification factors (sex, race and ethnicity, and number of risk factors) as fixed effects, and subject as a random effect. Comparisons of GT0918 to placebo for odds ratios (ORs), corresponding 95% CIs and p-values will be calculated at each visit.

Time to Sustained 100% SARS CoV-2 Viral Reduction

Time to sustained 100% SARS-CoV-2 viral reduction (in days) is defined as:

Date when sustained 100% SARS CoV-2 viral reduction is changed to 'Yes' - first dosing date + 1.

If a patient has not experienced SARS-CoV-2 clearance by completion or early discontinuation of study/study treatment, the patient will be censored at the date of their last visit during the post-treatment period.

Time to sustained 100% SARS CoV-2 viral reduction and will be summarized and plotted by treatment group with mITT set using the Kaplan-Meier (KM) method. The 2-sided 95% CIs for the 25th, 50th and 75th percentiles, as well as at days 3, 7, 14 and 28 using the Brookmeyer and Crowley method will be reported when estimable. P-value will be obtained from the log-rank test stratified by age, and sex, race and ethnicity, and number of risk factors at randomization. Hazard ratios and corresponding 95% confidence intervals will be obtained from a Cox proportional hazard model which treated treatment group as a unique covariate, and age, and sex, race and ethnicity, and number

of risk factors as stratas. The Cox proportional hazard model will be also performed by subgroup of duration since symptom onset to randomization category (≤ 3 days; > 3 days).

SARS CoV-2 Viral Clearance

SARS-CoV-2 Viral clearance (Yes/No) is defined when at least two consecutive negative tests proceed a positive test with all tests ≥ 24 hours apart. The date of viral clearance is defined as the earliest date between the consecutive negative tests.

The proportion of subjects that achieve SARS-CoV-2 clearance at Days 3, 7, 14, and 28 will be summarized by treatment in frequency tables, plotted and listed. Viral clearance can only be achieved (Yes) at days with a negative result. Generalized estimating equation (GEE) model will be used to model the proportions of achieving SARS-CoV-2 clearance at different visits. The model will consider treatment group, visit, treatment-by-visit interaction, age and stratification factors (sex, race and ethnicity, and number of risk factors) as fixed effects, and subject as a random effect. Comparisons of GT0918 to placebo for odds ratios (ORs), corresponding 95% CIs and p-values will be calculated at each visit.

Time to SARS-CoV-2 Clearance

Time to SARS-CoV-2 clearance (in days) is defined as:

Date when SARS-CoV-2 clearance status is changed to 'Yes' - first dosing date + 1.

If a patient has not experienced SARS-CoV-2 clearance by completion or early discontinuation of study/study treatment, the patient will be censored at the date of their last visit during the post-treatment period.

Time to SARS-CoV-2 clearance will be applying the same KM methods and Cox proportional hazard models introduced for the time to sustained 100% SARS CoV-2 viral reduction analysis.

Viral Load AUC

SARS-CoV-2 viral load area under the concentration-time curve (AUC) will be calculated according to the linear trapezoidal rule using the measured SARS-CoV-2 viral load-time values above the lower limit of quantification (LoQ) at Days 3, 7, 14 and 28. Per ICON central lab, LoQ is 59.9 copies/mL. No imputations of missing data will be conducted. No AUC(0-D28) values will be calculated when Day 1 pre-dose and/or Day 28 values are missing, or if there are more than 3 values missing in the profile. The AUC (0-D28) will be summarized and plotted by treatment group and listed.

Viral Resistance by Day 28

The proportion of viral resistance at day 28 will be summarized by treatment group and listed. The CMH chi-square test introduced for the primary endpoint analysis will be used to compare the difference of proportion of viral resistance between treatment groups by day 28.

Viral resistance is defined as when subjects:

- Are not able to show two consecutive negative test results via ddPCR testing by Day 28 without any missing scheduled tests, and/or

- Show a positive real-time ddPCR test result after two consecutive negative ddPCR test results, and/or
- A confirmed rise in SARS-CoV-2 RNA of ≥ 1 log10 after achieving nadir on treatment.

COVID-19 Ordinal Outcomes Scale

Below summaries will be provided using mITT set:

- The percentage of subjects at each clinical status using NIAID 8-point ordinal scale at Days 3, 7, 14, and 28
- Comparison of the proportion of NIAID ordinal scale by Days 3, 7, 14, and 28: ordinal generalized estimating equation (GEE) with treatment, age, stratification factors (sex, race and ethnicity, and number of risk factors), visit, and interaction of visit and treatment will be included in the model as fixed effects, and subject will be included as a random effect. Odds ratios with 95% confidence intervals and p-values will be presented. If data are too sparse for one level of the above factors, the factor will not be included in the statistical model/test to avoid convergence issue. Inferential analysis will only be performed if data warrants.
- Proportion of subjects worsening from baseline (worsening is defined as any worsening on the NIAID ordinal scale from baseline to Days 3, 7, 14, and 28)

Stacked bar plot by treatment group and visits at Day 1, 3, 7, 14 and 28 will be produced for NIAID ordinal scale. Also, mean value by treatment group will be plotted over time.

All NIAID ordinal scales through the study period will be listed in listing.

Other Analysis for Clinical Status

Below summaries for other analysis for clinical status will be provided as well:

- Summary of Hospitalization and Extended Care Facility Admissions by Day 28 (COVID-19 related will be summarized separately)
Note: Hospitalization (≥ 24 hours) includes: Hospitalization, Emergency room and ICU. Extended Care Facility Admittance is excluded.
 - Number and proportion of subjects hospitalized
 - Duration of Hospitalization
 - Number and proportion of subjects hospitalized by admission type: Hospitalization, Emergency Room, Intensive Care Unit (ICU) and Extended Care Facility
 - Duration by admission type
 - Comparisons of proportion of hospitalization between treatment group will be made using FIRTH logistic regression, with adjusting age and the stratification factors (sex, race and ethnicity, and number of risk factors). Odds ratios with 95% confidence intervals and p-values will be present. If data are too sparse for one level of the above factors, the factor will not be included in the statistical model/test to avoid convergence issue. Inferential analysis will only be performed if data warrants.
- Summary of New Oxygen Use by Day 28 (COVID-19 related will be summarized separately)
 - Number and proportion of subjects requiring any oxygen use
- Summary of COVID-19 Related Medical Attended Visits by Day 28
 - Proportion of subjects with COVID-19 related medical attended visits

All hospitalization events and COVID-19 related medical attended visits will be listed.

Time to Hospitalization

Time to Hospitalization (in days) is defined as:

First hospital admission date - first dosing date + 1.

Note: Hospitalization (≥ 24 hours) includes Hospitalization, Emergency room and ICU. Extended Care Facility Admittance is excluded.

The following two summaries will be generated separately:

- All-Cause Hospitalization
- COVID-19 Related Hospitalization

If a patient has not experienced hospitalization by completion or early discontinuation of study/study treatment, the patient will be censored at the date of their last visit during the post-treatment period.

Time to hospitalization will be evaluated up to Day 28 and will be summarized and plotted by treatment group with mITT set using the Kaplan-Meier (KM) method. The 2-sided 95% CIs for the 25th, 50th and 75th percentiles, as well as at days 3, 7, 14 and 28 using the Brookmeyer and Crowley method will be reported when estimable. P-value will be obtained from the log-rank test stratified by age, and sex, race and ethnicity, and number of risk factors at randomization. Hazard ratios and corresponding 95% confidence intervals will be obtained from a Cox proportional hazard model which treated treatment group as a unique covariate, and age, and sex, race and ethnicity, and number of risk factors as stratas. The Cox proportional hazard model will be also performed by subgroup of duration since symptom onset to randomization category (≤ 3 days; > 3 days).

If cases of hospitalization are too sparse (e.g., < 1 case in one treatment group), no time to hospitalization analyses will be performed.

Proportion of Symptom Resolution

All symptom resolution is defined as

all symptoms (those scored 0-3*) on the symptom questionnaire scored as absent (scored 0), with each symptom resolution absent for at least 48 hours.

Note: * Seven individual questions from COVID-19-Related Symptom Questionnaire are included here: questions 3, 4, 5, 6, 7, 8 and 9.

Additionally, all symptom resolution will be defined differently to include all individual questions scored 0-3 and related outputs will be noted as sensitivity analysis. It is defined as

all symptoms (those scored 0-3*) on the symptom questionnaire scored as absent (scored 0), with each symptom resolution absent for at least 48 hours.

Note: * Nine individual questions from COVID-19-Related Symptom Questionnaire are included here: questions 1 through 9.

The proportion of subjects with all symptom resolution will be performed at Days 3, 7, 14, and 28 by treatment in frequency tables and listed using mITT set. Generalized estimating equation (GEE) model will be fitted with the response of symptom resolution mapped to categories of Yes or No and with treatment, age, stratification factors (sex, race and ethnicity, and number of risk factors), time

effect and time*treatment interaction terms included in the model as covariates. Odds ratios with 95% confidence intervals and p-values will be present.

Total symptom score (seven individual questions from COVID-19-Related Symptom Questionnaire included here are questions 3, 4, 5, 6, 7, 8 and 9) and change from baseline in total symptom score to Days 3, 7, 11, 14 and 28 will be summarized by treatment group. Change from baseline will be compared using mixed model repeated measures (MMRM) with the fixed effects of baseline total symptom score, age and stratification factors (sex, race and ethnicity, and number of risk factors) and the random effect of subjects and with time effect and time*treatment interaction terms included in the model. Change from baseline in total symptom score will also be graphically displayed.

Additionally, total symptom score will be calculated differently to include nine individual questions (1 through 9) and related outputs will be noted as sensitivity analysis.

A summary of overall COVID-19 related symptoms, including overall symptoms severity, overall general physical health and returned to usual physical health, at Days 3, 7, 11, 14 and 28 will be provided in frequency table and listed.

Additionally, the proportion of subjects with at least 2 points decrease in symptom score (total of ratings) from baseline to Days 3, 7, 14 and 28 will be summarized and listed as well. Generalized estimating equation (GEE) model will be fitted with the response of at least 2 points decrease mapped to categories of Yes or No and with treatment, age, stratification factors (sex, race and ethnicity, and number of risk factors), time effect and time*treatment interaction terms included in the model as covariates. Odds ratios with 95% confidence intervals and p-values will be present.

Time to All Symptom Resolution

Time to all symptom resolution (in days) is defined as:

